10.4.2.2 Analysis of secondary and other efficacy endpoints

Continuous secondary and other efficacy endpoints: BPI-DPN scores and NPSI, measured at multiple time points, will be analyzed using a similar modeling strategy as used for the primary endpoint.

Categorical secondary endpoints: PGIC, Proportion of responders based on Question 5 of BPI-DPN will be compared between treatment groups using a Cochran-Mantel-Haenszel test stratified by the randomization factor of Baseline pain severity. Patients with missing measurement at Week 6 will be considered non-responders. A nonresponder imputation (NRI) rule will be applied for all analyses based on categorical variables to assign outcomes to missing observations. The percentage of patients who need rescue medication and prematurely dropout

will be summarized descriptively. The Kaplan-Meier methods will be used to generate statistical summaries of the time to loss of efficacy variable among patients who achieve \geq 30% reduction in ADPS based on Question 5 of the BPI-DPN from Week 6 and Week 11.

The qualitative patient interview substudy will be managed by a vendor (RTI-Health Solutions, Research Triangle Park, NC). The data analysis methods will be detailed in a separate statistical analysis plan and results will be reported separately.

Multiplicity

The 2 pairwise comparisons of each LX9211 dose levels vs placebo will be performed using Dunnett's test. Testing among the secondary endpoints will not be adjusted for multiplicity, and hence, the analyses will be exploratory. Other endpoints will likewise not be adjusted for multiple testing. Adjusted and unadjusted p-values will be presented.

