7.6.2.5 Patient Global Impression of Change (PGIC) at Week 6

The PGIC, a 7-point rating scale, will assess the patient's belief about their overall improvement experienced at the end of treatment.

The frequency and percentages of patients within each category at Week 6 will be presented by treatment group. The treatment effect will be evaluated using an

ANOVA model with treatment and randomization stratum of Baseline pain severity (moderate, severe) as independent variables. Least-square means of PGIC in each treatment group and the difference between LX9211 and placebo for each comparison, along with their 95% CIs and p-value will be presented.

7.6.2.6 Time to loss of efficacy from Week 6 to Week 11 among patients achieving $\geq 30\%$ reduction in pain intensity in ADPS based on Question 5 of the BPI-DPN at Week 6

Time to loss of efficacy is defined as the time from the date of Week 6 visit to the date of termination of safety follow-up due to lack of efficacy. Termination of safety follow-up due to other reasons and death are competing risk. Patients who have terminated the safety follow-up due to any reason other than lack of efficacy after Week 6 visit or have completed the study through Week 11 will be censored at the date of the last ADPS assessment based on Question 5 of the BPI-DPN collected by patients in the daily pain dairy.

Time to loss of efficacy (weeks) = (date of termination of safety follow-up due to lack of efficacy or censoring – date of Week 6 visit + 1) / 7.

Only patients who achieved $\geq 30\%$ reduction in pain intensity in ADPS based on Question 5 of the BPI-DPN from Baseline to Week 6 will be included in the analysis of time to loss of efficacy.

Kaplan-Meier estimates and the associated 95% CIs of the median, 25th, and 75th percentile will be presented. The 2-sided 95% CIs will be computed using the log-log transformation.

The minimum and maximum time to loss of efficacy (using censored and event times) will also be presented.

The survivor function will be displayed graphically by treatment group using a KM curve.

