7.6.3 Sensitivity Analysis

In the event that rescue medication is used, a supplementary MMRM model will be applied to the primary endpoint dataset that excludes data collected after the initiation of the rescue medication using the mITT population. This model will be parameterized in the same manner as will be used for the primary analysis of this endpoint.

In addition, to assess the robustness of the MMRM analyses performed under the MAR assumption, and given the long half-life of LX9211, PMMs with copy reference-based imputation methods will be applied on both datasets (with and without data collected after the initiation of the rescue medication) using the mITT population.

CONFIDENTIAL

Document Date: 07JUN2022

Page 32 of 55

ST-AD-008 version 05

Methods will be adopted to estimate for both non-monotone and monotone missing data patterns. Imputations for the non-monotone missing data pattern will be the initial step. The imputation algorithm based on Monte Carlo Markov Chain methodology will be used assuming a MAR mechanism for the missing data; 100 imputations will be used. Then multiple imputations will be performed to assign the response variable at consecutive study weeks in a sequential manner for the monotone missing data pattern. For this chain-based method, control-based imputation will be applied so that there is no direct use of observed data from the LX9211 treatment groups in estimating the imputation model. The method is derived such that it builds its imputation only on the placebo group data. The imputed datasets will be combined by use of Rubin's rule and analyzed using an analysis of covariance (ANCOVA) model fitted for the fixed effects of treatment, the randomization stratum of the Baseline pain severity (moderate, severe), and the continuous fixed covariate of Baseline score. The ANCOVA analysis will be performed at Week 6 only. Summary statistics from applying the ANCOVA model across the multiple imputed datasets will be combined to obtain an overall estimate of the treatment group differences.

Sensitivity analyses are not planned for analyses of the secondary or other efficacy endpoints.

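### SAP 7.6.2.6 names other terminations and death as competing risks but censors them and plans only Kaplan-Meier, so one minus the curve is not the probability of the event as the SAP defines it

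*SAP*

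**What the plan says.** SAP 7.6.2.6 restricts the analysis to patients with at least a 30% ADPS reduction at Week 6. The clock starts there: "Time to loss of efficacy is defined as the time from the date of Week 6 visit to the date of termination of safety follow-up", and only a termination for lack of efficacy counts as the event.

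The next sentence is "Termination of safety follow-up due to other reasons and death are competing risk". The one after it pools these patients with those who reach Week 11, and all of them "will be censored at the date of the last ADPS assessment" found in the diary. The time formula has room only for an event date or a censoring date, so the named competing events have no status of their own.

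The planned output is: "Kaplan-Meier estimates and the associated 95% CIs of the median, 25th, and 75th percentile will be presented", with log-log intervals, and "The survivor function will be displayed graphically by treatment group using a KM curve". Protocol 10.4.2.2 names the same method: "The Kaplan-Meier methods will be used to generate statistical summaries of the time to loss of efficacy variable". Neither document plans a cumulative incidence function. SAP 7.6.3 closes off any other check: "Sensitivity analyses are not planned for analyses of the secondary or other efficacy endpoints".

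**The concern.** Two consecutive sentences of the SAP pull in different directions. Calling an occurrence a competing risk says that it prevents the event. Censoring it in a Kaplan-Meier analysis treats the patient as still able to have the event and represented by those who remain. Because the event is itself a termination of follow-up, the first description is the right one for this definition: follow-up can be terminated only once.

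A reader of the Kaplan-Meier curve would naturally take one minus its height at Week 11 as the share of Week 6 responders who stopped for lack of efficacy. If other terminations occur along the way, the true share is lower. The percentiles shift with it, to earlier times. Nothing else in the plan would show the difference.

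**Working it through.** The documents state no figure for this endpoint, so there is none to reproduce. They also give no rates for either kind of termination. Every size below is an assumption shown over a range.

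**Inputs.** Follow-up is 5 weeks (Week 6 to Week 11). Hazards are assumed constant. Let h1 be the cumulative hazard of lack-of-efficacy termination over the 5 weeks, and h2 that of all other terminations including death.

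**Formulas.**
- Kaplan-Meier with other terminations censored: 1 − KM = 1 − exp(−h1)
- Actual probability of the event: CIF = h1/(h1 + h2) × [1 − exp(−(h1 + h2))]

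**Base case, h1 = 0.10.** 1 − KM = 1 − exp(−0.10) = 9.5%, whatever h2 is. For h2 = 0.30, CIF = (0.10/0.40) × [1 − exp(−0.40)] = 0.25 × 0.330 = 8.2%.

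| h2 | 1 − KM | CIF | Excess (points) | Relative excess |
|---|---|---|---|---|
| 0.05 | 9.5% | 9.3% | 0.2 | 2.5% |
| 0.10 | 9.5% | 9.1% | 0.5 | 5.0% |
| 0.20 | 9.5% | 8.6% | 0.9 | 10.2% |
| 0.30 | 9.5% | 8.2% | 1.3 | 15.5% |

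With h1 also varied from 0.05 to 0.30, the relative excess runs from 2.4% to 15.6%.

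**Higher event rate, 1 − KM = 30%.** Here the other terminations are given as net probabilities, p2 = 1 − exp(−h2), over 5 weeks.

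| p2 | CIF | Excess (points) | Relative excess |
|---|---|---|---|
| 5% | 29.3% | 0.7 | 2.4% |
| 10% | 28.6% | 1.4 | 5.0% |
| 20% | 27.1% | 2.9 | 10.8% |
| 30% | 25.5% | 4.5 | 17.6% |

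The 25th percentile from Kaplan-Meier is 5 × ln(0.75)/ln(0.70) = 4.03 weeks. From the cumulative incidence it is 4.13 weeks at p2 = 5% and 4.86 weeks at p2 = 30%. In the base case, at 9.5%, no planned percentile would be expected to be reached, and only the curve is affected.

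**Check on patient-level data.** Take an arm of 40 with 8 lack-of-efficacy terminations. The share with the event is 8/40 = 20.0%, and the Aalen-Johansen estimate returns 20.0% in every case. With 0, 2, 4 or 8 other terminations spread among the events, 1 − KM is 20.0%, 21.0%, 21.9% or 22.9%. In 2,000 randomly generated data sets of 40 patients with both kinds of termination, 1 − KM exceeded the Aalen-Johansen estimate every time.

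**The case against.** The strongest defence is that Kaplan-Meier with other causes censored is a recognised cause-specific analysis. It estimates a net risk: what would be seen if other terminations did not occur, provided they are independent of loss of efficacy. The protocol names the method and the SAP follows it. This defence stands as a description of what Kaplan-Meier can estimate. But the SAP states neither that target nor the independence assumption, and it labels the events as competing risks.

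A second argument is that the protocol lists the endpoint simply as time to loss of efficacy. Withdrawing consent does not stop pain from returning; it stops us observing it. Under a diary-based event, most other terminations would be ordinary censoring and only death would preclude the event. That is fair, and it marks the limit of the point: it applies to the event as SAP 7.6.2.6 now defines it.

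A reader might go further and infer that Kaplan-Meier makes the comparison between arms unfair when dropout differs. The documents do not support that. Two arms with the same h1 = 0.10 but h2 of 0.05 and 0.30 both show 9.5% on Kaplan-Meier, while the cumulative incidence separates them at 9.3% and 8.2%. The two answer different questions, and neither is the fair one by default. Nor is the excess always larger in absolute terms in the arm with more other terminations. At 30% lack of efficacy and 5% other it is 0.71 points; at 5% and 10% it is 0.25. The gradient needs equal lack-of-efficacy hazards or a relative scale. Differential dropout for tolerability is also speculative here, since follow-up tablets are placebo in every arm, although mean half-lives of 6 to 8 days (Protocol 3.3) leave some residual drug.

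**Conclusion.** The point holds in a limited form. For the event that SAP 7.6.2.6 defines, one minus Kaplan-Meier overstates the actual probability whenever other terminations precede later events. The estimator does not match the SAP's own competing-risk sentence, and no other section resolves this.

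The size is modest and rests wholly on assumed rates and constant hazards: about 0.2 to 1.3 points at a cumulative event hazard of 0.10, and about 1.5 points or less if lack of efficacy is at most 30% and other terminations at most 10%. At equal lack-of-efficacy hazards the excess grows with the rate of other terminations.

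Secondary endpoints are exploratory (SAP 7.6), and 7.6.2.6 specifies no between-arm test and no Week 11 probability. This is a worthwhile improvement and does not threaten the trial's conclusions.

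**What to change.** In SAP 7.6.2.6, report the Aalen-Johansen cumulative incidence of lack-of-efficacy termination by arm, with a Week 11 estimate and 95% CI. Count terminations for other reasons and death as competing events at their own dates, not at the last diary entry, and censor only patients who complete Week 11. Keep the protocol's Kaplan-Meier output only as a supplement, labelled as net risk under independent censoring. Record the change in SAP Section 8, which at present lists only the NPSI model.

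Rewording alone, by dropping the competing-risk sentence and stating the net-risk target, would remove the contradiction but still leave the actual probability unreported.

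The cost is a short SAP edit, one extra output from a standard procedure, and a small departure from the protocol's named method on an exploratory endpoint. No new data are needed: Protocol 6.3 already requires the discontinuation date and the primary reason for ending participation to be recorded.

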7.6.3 Sensitivity Analysis

In the event that rescue medication is used, a supplementary MMRM model will be applied to the primary endpoint dataset that excludes data collected after the initiation of the rescue medication using the mITT population. This model will be parameterized in the same manner as will be used for the primary analysis of this endpoint.

In addition, to assess the robustness of the MMRM analyses performed under the MAR assumption, and given the long half-life of LX9211, PMMs with copy reference-based imputation methods will be applied on both datasets (with and without data collected after the initiation of the rescue medication) using the mITT population.

CONFIDENTIAL

Document Date: 07JUN2022

Page 32 of 55

ST-AD-008 version 05

Methods will be adopted to estimate for both non-monotone and monotone missing data patterns. Imputations for the non-monotone missing data pattern will be the initial step. The imputation algorithm based on Monte Carlo Markov Chain methodology will be used assuming a MAR mechanism for the missing data; 100 imputations will be used. Then multiple imputations will be performed to assign the response variable at consecutive study weeks in a sequential manner for the monotone missing data pattern. For this chain-based method, control-based imputation will be applied so that there is no direct use of observed data from the LX9211 treatment groups in estimating the imputation model. The method is derived such that it builds its imputation only on the placebo group data. The imputed datasets will be combined by use of Rubin's rule and analyzed using an analysis of covariance (ANCOVA) model fitted for the fixed effects of treatment, the randomization stratum of the Baseline pain severity (moderate, severe), and the continuous fixed covariate of Baseline score. The ANCOVA analysis will be performed at Week 6 only. Summary statistics from applying the ANCOVA model across the multiple imputed datasets will be combined to obtain an overall estimate of the treatment group differences.

Sensitivity analyses are not planned for analyses of the secondary or other efficacy endpoints.

7.6.4 Subgroup Analysis

The primary endpoint will be analyzed using the mITT population for the following subgroups:

- Baseline pain severity based on the actual stratum, moderate or severe
- Sex, male or female
- DPNP drug use, yes or no
- Subjects who experience the 5 specific TEAEs, yes or no

DPNP drug use subgroup is defined as those who took concomitant DPNP medications including the following: pregabalin, gabapentin, duloxetine, amitriptyline, venlafaxine, desvenlafaxine, valproic acid.

The 5 specific TEAEs refer to the AEs: dizziness, headache, nausea, somnolence, and balance disorder, which usually occur more frequently than other AEs.

The same MMRM covariates used for the primary endpoint analysis will be used for the subgroup analyses except that for the Baseline pain severity subgroup analysis, the randomization stratum of Baseline pain severity (moderate, severe) will not be included as a covariate. A forest plot of the LS Means difference and 95% CI for the

comparison of LX9211 versus placebo with the change from Baseline scores will be presented for all subgroups.

All subgroup analyses will be exploratory.

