10.1 Determination of Sample Size

Proposed Sample Size

A sample size of 75 patients per treatment group who complete the 6-week double-blind Treatment Period will yield 80% power to detect a true mean difference of 1 unit between at least 1 of LX9211 treatment groups and placebo in ADPS change from Baseline, assuming a common standard deviation of 2 and an overall significance level of α=0.05 (2-sided Dunnett's test). Accounting for a dropout rate of 20%, a total of 282 patients (94 patients per treatment group) will be enrolled and randomly assigned to treatment in a 1:1:1 ratio. This sample size is adjusted for the multiple comparisons of each LX9211 treatment group with placebo (Westfall, 1999).

Sample Size Reestimation

Due to the uncertainty in the outcome for the primary endpoint analysis secondary to potential variations in some of the key design parameters such as the dropout rate and standard deviation associated with the targeted treatment group difference, an unblinded SSR adaptation will be implemented at the time of the interim analysis testing for futility. This will occur when the first 141 patients have been accrued and followed thru Week 6 or dropped out early from the trial (whichever event happens first). Should a patient drop out early in the study, but return for the Week 6 visit, the Week 6 data will be used in the analysis. The Chen-DeMets-Lan method will be used for the unblinded SSR since it requires minimal change from a group sequential test. This method requires specification for a number of criteria related to the allowable conditions for increasing the sample size that ensures that ordinary group sequential methods can be applied while seeing that the overall error is not inflated compared to the original group sequential design. The 2 primary conditions which are required and satisfied in the SSR for this study are that (a) the SSR is made at the penultimate look, and (b) the conditional power at the penultimate look occurs between 50% and 80.3% (the original specified power under the group sequential design). The SSR is linked to the projected effect size falling within this "promising" or "favorable" range of conditional power. Having satisfied these 2 main conditions, the Type I error rate after increasing the sample size until the conditional power equals the original target power will not be greater than the Type I error from the originally proposed design.

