Analysis and summarization of treatment group comparisons for the safety endpoints will be reported in their original measurement units and converted values to accommodate regulatory review by the Food and Drug Administration and external authorities, where appropriate.

All significance tests will be 2-sided and use a 0.05 α -level unless specified otherwise.

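### The planned subgroup analysis shows an effect for each level but never estimates the difference in effect between levels

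*SAP*

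**What the plan says.** SAP 7.6.4 analyses the primary endpoint in the mITT population by four two-level factors: baseline pain severity (actual stratum), sex, DPNP drug use, and occurrence of any of five named TEAEs. On the model it says: "The same MMRM covariates used for the primary endpoint analysis will be used for the subgroup analyses". The one exception is that the randomization stratum is left out when pain severity is the subgroup.

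The covariates carried over from SAP 7.6.1 are treatment, week, treatment by week, severity stratum and Baseline ADPS. None of them is a subgroup or treatment-by-subgroup term.

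The specified output is "A forest plot of the LS Means difference and 95% CI" for LX9211 against placebo in each subgroup. Protocol 10.4.4 names severity and sex, leaves further subgroups to the SAP, and adds no interaction estimate. Both documents call these analyses exploratory.

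**The concern.** A subgroup display is read to learn whether the effect differs between levels. The plan gives two effects and two intervals per factor and leaves the comparison to the eye. The easy visual comparison is whether each interval crosses zero. One interval excluding zero while the other includes it is not evidence that the effects differ. It happens often when the effects are equal and each level holds only part of the sample.

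Severity is the randomization stratum, and severity and sex are the two subgroups the protocol itself names, so these rows will be looked at. A difference with its interval would show how little the trial can say about effect modification. The planned plot does not print that.

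**Working it through.** **Inputs.** From Protocol 10.1: "A sample size of 75 patients per treatment group who complete the 6-week double-blind Treatment Period", giving "80% power to detect a true mean difference of 1 unit", "assuming a common standard deviation of 2 and an overall significance level of α=0.05 (2-sided Dunnett's test"). From SAP 7.1: "All significance tests will be 2-sided and use a 0.05" level unless otherwise specified, which matches the 95% CIs on the plot. The subgroup split is in neither document, so 50:50, 67:33 and 75:25 are assumed.

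**The plan's own figure.** The noncentrality is 1 / (2 × √(2/75)) = 3.062. The two-sided Dunnett critical value for two comparisons with 222 df, obtained by simulation, is 2.224. Power per comparison is then 79.8%, or 80.8% for at least one rejection if only one dose works. Dropout: 75 / 0.80 = 93.75, rounded up to 94, and 3 × 94 = 282. The stated 80% and 282 reproduce.

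**One interval excludes zero and the other does not.** This is for one factor and one dose, with the same true effect in both levels. A level holding a fraction f of each arm has 75f completers per arm. Let a and b be the two-sample t power (two-sided 0.05, SD 2) in the two levels. The levels contain different patients, so P(exactly one excludes zero) = a(1 − b) + b(1 − a).

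At a true effect of 1:

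| Split | n per arm in each level | a, b | P(exactly one) |
|---|---|---|---|
| 50:50 | 37.5, 37.5 | 0.570, 0.570 | 0.49 |
| 67:33 | 50.25, 24.75 | 0.699, 0.407 | 0.54 |
| 75:25 | 56.25, 18.75 | 0.748, 0.319 | 0.59 |

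For 50:50: 2 × 0.570 × 0.430 = 0.490.

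At 50:50, varying the true effect:

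| True effect | Power per level | P(exactly one) |
|---|---|---|
| 0 | 0.050 | 0.095 |
| 0.5 | 0.188 | 0.30 |
| 1 | 0.570 | 0.49 |
| 1.25 | 0.761 | 0.36 |
| 1.5 | 0.893 | 0.19 |

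With 94 per arm instead of 75, at a true effect of 1 and 50:50, power per level is 0.67 and the probability is 0.44.

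**What a direct estimate would give.** The SE of the difference between two level-specific effects is 2 × √(2/(75f) + 2/(75(1 − f))).

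| Split | SE | 95% half-width (1.96 × SE) |
|---|---|---|
| 50:50 | 0.653 | 1.28 |
| 67:33 | 0.695 | 1.36 |
| 75:25 | 0.754 | 1.48 |

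If the true effects are equal, a 95% CI for this difference wrongly excludes zero in 5% of trials. At 50:50, power to detect a true between-level difference of 1 point is about 33%. The difference detectable with 80% power is (1.96 + 0.8416) × 0.653 = 1.83 points.

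**The case against.** The strongest reply is that nothing essential is lost. The two levels of a factor are disjoint, so a reader can subtract the plotted estimates, recover the standard errors from the intervals, and obtain an approximate difference with a CI. Anyone who looks instead for non-overlapping intervals would rarely be misled: with equal effects and an even split, the two 95% CIs fail to overlap in only about 0.6% of trials. This stands. A reader might infer that heterogeneity cannot be judged from the plot, and the documents do not support that.

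Other limits also stand:

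- A reader might take the 49% as a general rate. It applies to one factor and one dose, at the design effect, with an assumed even split. It also comes from an unadjusted t test on completers, not from the planned covariate-adjusted MMRM in the mITT population.
- The SAP does not say that a separate model is fitted in each level. That is the most natural reading of an unchanged covariate list with the stratum removed for severity. However, a pooled model would also need to drop the stratum beside a nearly identical severity factor.
- Nothing in the documents ties a decision on a later population to a subgroup result, and the exploratory label is already there.
- An interaction test would have low power, and a non-significant result could be misread as homogeneity. This is a reason to report an estimate with its interval rather than rely on a p-value.

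The gap remains on either reading of the model: no between-level difference, and no interval for it, is prespecified or reported.

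**Conclusion.** The point holds as a modest reporting improvement. SAP 7.6.4 plans level-specific effects with 95% CIs and no estimate of the treatment-by-subgroup difference, and Protocol 10.4.4 does not supply one.

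The 49% to 59% range rests on 75 completers per arm, SD 2, a true effect of 1 in both levels, and assumed splits from 50:50 to 75:25. It counts one factor and one dose. Away from the design effect, at an even split, the figure is lower.

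The documents do not support a claim that the planned analysis is invalid or that it will produce a false subgroup claim. They do support saying that the relevant contrast is left to hand calculation. Its interval would also be wide: the half-width of 1.28 to 1.48 points exceeds the 1-point effect the trial was sized to detect.

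**What to change.** In SAP 7.6.4, for the baseline subgroups, fit one MMRM per factor to all mITT patients. Include treatment, week, subgroup, and all their two-way and three-way interactions, plus the primary covariates. When severity is the subgroup factor, leave out the randomization stratum, as the SAP already does, because the two are nearly the same variable.

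The baseline subgroups are pain severity and sex. DPNP drug use belongs with them if it is defined by use at baseline. SAP 7.4 lists it as a baseline characteristic, but 7.6.4 defines it by concomitant medication, which under 7.4.2 can include drugs started after the first dose.

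For each dose, report at Week 6 the difference in treatment effect between levels with its 95% CI. Print it beside the forest plot and mark it exploratory. An interaction p-value is optional. If one is given, state that a non-significant result is not to be read as equal effects.

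The cost is one extra model per factor and an imprecise estimate, with a half-width of about 1.3 to 1.5 points under the assumptions above. The change does not repair the TEAE subgroup: that factor is defined by events after randomization, and an interaction term does not remove that problem.
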